| Comprehensive Metabolic Profile (CMP)                     | X               | X                                      |  | X                                       | X                                |                           | X   |
| Amylase and Lipase  | X               | X                                      |  |   |                                  |                           | X   |
| GGT and Magnesium level                                   | X               |  |  |   |                                  |                           | X   |
| PT/INR and aPTT   | X               |  |  |   |                                  |                           | X   |
| Thyroid Function (TSH, T4, free T3)           | X               | X                          |  |   |                                  |                           | X   |
| Pregnancy test (serum or urine) (WOCBP)       | X               |  |  |   |                                  |                           | X   |
| Hepatitis B and C and HIV                     | X               |  |  |   |                                  |                           |   |
| Urinalysis                                    | X               |  |  |   |                                  |                           | X   |
| DISEASE ASSESSMENT                                 |                 |  |  |   |                                  |                           |   |
| CT of chest                                   | X               | X                          |  | X                           | Every 3
months
(± 7 days)  |                           | X   |
| CT or MRI of abdomen and pelvis               | X               | X                          |  | X                           |                                  |                           | X   |
| Bone scan in subjects with bone metastases    | X               | X                          |  | X                           |                                  |                           | X   |
| TREATMENT EXPOSURE                                 |                 |  |  |   |                                  |                           |   |

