**Key to Footnotes**

- 1: Medical History includes: smoking history questionnaire and a question regarding how the patient heard about the study. Prior anti-cancer treatment should be documented including medications (chemotherapy, checkpoint inhibitors, etc) radiation or surgery. Antibiotic use for 6 months prior to stool collection will be documented. Diagnosis and staging to include pathology report and Tumor Node Metastasis (TNM) staging. Prior genomic or molecular testing results are required if available.
- 2: Vital signs to include: blood pressure, pulse, temperature, respiration rate, weight, height (screening only) and ECOG performance status. Please see Section 5 for guidelines regarding vital signs during study drug infusion.
- 3: Resting 12-lead ECGs will be recorded at screening and as clinically indicated throughout the study. ECGs should be obtained after the patient has been in a supine position for 5 minutes and recorded while the patient remains in that position. In case of clinically significant ECG abnormalities, including a QTcF value >470 ms, 2 additional 12-lead ECGs should be obtained over a brief period (eg, 30 minutes) to confirm.
- 4: Thyroid Function (TSH, T4 and T3) will be done prior to treatment C1D1 then C3D1, C5D1, and C7D1 or more often if clinically indicated per site investigator discretion. For T4 and T3, free versus total is at the discretion of the site investigator.
- 5: For women of childbearing potential (WOCBP): urine or serum  $\beta$ hCG if clinically appropriate. If a urine test is done and it is positive or cannot be confirmed as negative, a serum pregnancy test will be required.
- 6: Active infection, including tuberculosis (clinical evaluation that includes clinical history, physical examination and radiographic findings, and tuberculosis testing in line with local practice), hepatitis B, hepatitis C, or human immunodeficiency virus (HIV, positive HIV 1 or 2 antibodies). Active hepatitis B virus (HBV) infection is defined by a positive HBV surface antigen (HBsAg) result. Subjects with a past or resolved HBV infection (defined as the presence of hepatitis B core IgG antibody and the absence of HBsAg, deoxyribonucleic acid [DNA] negative) are eligible. Subjects positive for hepatitis C virus (HCV) antibody are eligible only if polymerase chain reaction is negative for HCV ribonucleic acid (RNA).

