12: Blood samples for research will be drawn pre-treatment C1D1 (may be done during screening if subject is found eligible), C2D1, C3D1, C6D1 and at time of progression. See Table 3 and CLM for additional information. Blood samples for research will be collected for subjects receiving re-treatment after progression. If samples are collected at progression after the initial 7 cycles of tremelimumab, samples at screening prior to re-treatment C1D1 do not need to be repeated. Samples will also be done prior to treatment C2D1, C3D1, C6D1 and at progression after re-treatment.

13. Stool for microbiome analysis will be collected prior to treatment prior to C1D1 of initial treatment. Subjects will be provided a kit with detailed instructions regarding collection of the sample prior to the timepoint. Samples will not be collected during re-treatment. Please see the CLM for additional details.

14: The safety follow-up visit should only occur when subjects stop study treatment for whatever reasons (toxicity, progression, or at discretion of site investigator) and should be performed ~30 days (+7 days) after the last dose of treatment. Subjects who have an ongoing Grade  $\geq 2$  or serious AE (SAE) at this visit will continue to be followed until the AE resolves to  $\leq$  Grade 1 or baseline, deemed clinically insignificant, and/or until a new anti-cancer treatment starts, whichever is earlier.

15: Subjects completing study treatment without evidence of disease progression will be followed every 3 months for progression. Subjects with disease progression within 1 year of completing initial treatment with tremelimumab may be eligible for re-treatment with tremelimumab. After progression for subjects who are not candidates for tremelimumab retreatment or who initiate other anticancer therapies, patients will be followed for survival which may be accomplished via clinic visit, phone call, or other avenues as appropriate. Subjects who decline to return to the site for evaluations will be offered follow-up by phone every 3 months as an alternative.

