### 11.1.3 Adverse Events of Special Interest

An adverse event of special interest (AESI) is one of scientific and medical interest specific to understanding of the study drug(s) and may require close monitoring and rapid communication by the site investigator to the sponsor-investigator. An AESI may be serious or non-serious. The rapid reporting of AESIs allows ongoing surveillance of these events in order to characterize and understand them in association with the use of the study drug(s). If any AESI occurs in the course of the study, then the site investigators or other site personnel should report to Hoosier Cancer Research Network (HCRN) **within 1 business day** of becoming aware of the event.

HCRN will report to AstraZeneca **within 1 business day** of becoming aware of the event. AESIs for tremelimumab include, but are not limited to, events with a potential inflammatory or immune-mediated mechanism and that may require more frequent monitoring and/or interventions such as steroids, immunosuppressants, and/or hormone replacement therapy. These AESIs are being closely monitored in clinical studies with tremelimumab therapy.

An imAE is defined as an AE that is associated with drug exposure and is consistent with an immune-mediated mechanism of action and where there is no clear alternate etiology. Serologic, immunologic, and histologic (biopsy) data, as appropriate, should be used to support an imAE diagnosis. Appropriate efforts should be made to rule out neoplastic, infectious, metabolic, toxin, or other etiologic causes of the imAE. In the event of imAE or suspected imAE, the sponsor-investigator may request relevant clinical information (including images) for those subjects who demonstrate the event and may request the independent review by external experts based on the acquired clinical information.

If the site investigator has any questions with regards to an AE being an imAE, the site investigator should immediately contact the sponsor-investigator.

AESIs observed with tremelimumab include the following:

- Diarrhea/Colitis and intestinal perforation
- Pneumonitis/Interstitial Lung Disease (ILD)
- Hepatitis/transaminase increases
- Neuropathy / neuromuscular toxicity (e.g. Guillain-Barré, and myasthenia gravis)
- Endocrinopathy (ie, events of hypophysitis, adrenal insufficiency, and hyperthyroidism and hypothyroidism, Type I diabetes)
- Rash/Dermatitis
- Nephritis/Blood creatinine increases

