### 12.4 Assessment of Safety

The safety population will be defined as any patients that receive at least one dose of tremelimumab and will be used in the assessment of toxicity. Safety will be determined according to the NCI Common Terminology Criteria for Adverse Events (NCI CTCAE) v4.03. All subjects will be evaluable for adverse event evaluation from the time of their first dose of study treatment.

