### 12.6.2 Analysis Plans for Secondary Objectives

Any subject who receives at least one dose of treatment on this protocol is evaluable for toxicity. Toxicity rates will be summarized using frequency tables. Disease control rates will be analyzed based on the exact binomial test. Duration of response will be the time from the first documentation of response to the time of progression or death will be summarized using frequency tables. Progression free survival and overall survival curves will be based on the Kaplan-Meier method.

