### 12.6.3 Analysis Plans for Exploratory Objectives

To explore the relationship between PD-L1 expression and response to treatment, Fisher's exact test will be used. To explore the relationship between molecular subtype of bladder cancer and response to treatment, frequency tables will be constructed and Fisher's exact test will be used. To explore the relationship between genomic alterations, including mutational load, and changes in circulating immune biomarkers and response to treatment both Fisher's exact test and T-test will be used. Exploratory analyses correlating clinical outcomes and adverse events with stool microbiome diversity/composition as well as assessment of metabolomics and metagenomic whole genome sequencing may also be performed.

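### No thyroid test is scheduled after the first dose until C3D1 or at the safety visit, and no amylase/lipase after the last dose, yet every dosed subject stays in the toxicity denominator

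*Combined protocol and SAP*

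**What the plan says.** In the Section 7 calendar, the row beginning "Thyroid Function (TSH, T4, free T3" is marked at screening, on Day 1 of Cycles 1-7 (subject to footnote 4) and at screening for re-treatment. It is blank at Day 15, the safety visit, follow-up and progression. Footnote 4 says that the test "will be done prior to treatment C1D1 then C3D1, C5D1, and C7D1 or more often if clinically indicated", at the investigator's discretion.

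Amylase and lipase are marked at screening, on Day 1 of every cycle and at screening for re-treatment, but not at the safety visit. The row beginning "Comprehensive Metabolic Profile (CMP" is marked at the safety visit and at follow-up, as is CBC. Footnote 14 says that the safety visit "should be performed ~30 days (+7 days) after the last dose of treatment".

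On the analysis side, Section 12.4 states: "The safety population will be defined as any patients that receive at least one dose of tremelimumab". Section 12.6.2 adds: "Toxicity rates will be summarized using frequency tables". Neither section says how to treat a dosed subject who was never tested after dosing. Section 11.1.3 lists, among the events of special interest, the item beginning "Endocrinopathy (ie, events of hypophysitis, adrenal insufficiency, and hyperthyroidism and hypothyroidism, Type I diabetes", and also pancreatitis with lipase and amylase increases.

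**The concern.** Two event classes that the protocol singles out for close watching depend partly on blood tests, and the number of scheduled tests depends on how long a subject stays on drug. A subject who leaves early contributes to the denominator but may have had no scheduled opportunity to contribute to the numerator. In the frequency tables, an untested subject cannot be told apart from one who was tested and found normal.

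Two things are at stake: the completeness of the safety description, which is a secondary objective resting on about 28 subjects, and an abnormality in an individual subject that goes unnoticed after the last dose.

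**Working it through.** The plan states no thyroid or pancreatic event rate and no early-stopping rate, so there is no figure to reproduce. The check is of the schedule.

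**1. Visit days.** Cycle length is 28 days (Section 7). C1D1 = day 1, C2D1 = 1 + 28 = day 29, C3D1 = 1 + 56 = day 57 (±3).

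**2. Safety visit, 30 to 37 days after the last dose.** After one dose: 1 + 30 to 1 + 37 = days 31 to 38. After two doses: 29 + 30 to 29 + 37 = days 59 to 66. Neither assay is marked at this visit.

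**3. Time left after the last scheduled test.** Section 11.2.1 records adverse events until 30 days after stopping drug (or until new anticancer therapy, if sooner). For a subject given *k* doses, counting from the first dose:

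- window = 28(*k* − 1) + 30 days;
- last thyroid test at 28(*m* − 1), where *m* is the largest odd number not above *k*;
- last amylase/lipase at 28(*k* − 1).

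Assumptions: Day 1 samples precede that day's dose, and no sample is drawn for a cycle that is not started.

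| Doses | Window (days) | Last thyroid test | Days left | Last amylase/lipase | Days left |
|---|---|---|---|---|---|
| 1 | 30 | 0 (pre-dose) | 30 | 0 (pre-dose) | 30 |
| 2 | 58 | 0 (pre-dose) | 58 | 28 | 30 |
| 3 | 86 | 56 | 30 | 56 | 30 |
| 4 | 114 | 56 | 58 | 84 | 30 |
| 5 | 142 | 112 | 30 | 112 | 30 |
| 6 | 170 | 112 | 58 | 140 | 30 |
| 7 | 198 | 168 | 30 | 168 | 30 |

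For thyroid, the whole window after one or two doses is without a scheduled test. For amylase/lipase, the same is true after one dose. Every other subject has a final stretch of 30 or 58 days without one.

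**4. Exposure in that stretch.** Section 1.5 gives a terminal half-life of 22.1 days. Under simple exponential decline, 0.5^(30/22.1) = 0.39 of the last dose remains at day 30, so the stretch is not drug-free.

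**5. Which events can be lost.** Section 11.1.1 makes a laboratory abnormality an adverse event only if it causes signs or symptoms or needs treatment or further tests. Section 11.2.1 does not collect asymptomatic abnormalities that need no treatment. The affected class is therefore narrow: events that are silent or have non-specific symptoms, but would need treatment or further tests if found. Symptoms are an imperfect trigger. Appendix 1 describes headache, fatigue and weakness as non-specific signs of endocrinopathy, and Section 10.1.4 lists headache, fatigue and asthenia among the very common adverse events.

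**6. How far a few untested subjects move a rate.** Both inputs here are assumptions: 3 thyroid events, all in tested subjects, and *u* of 28 subjects untested. The plan's rate is 3/28 = 10.7% (exact 95% CI 2.3 to 28.2%). Among tested subjects it is 3/25 = 12.0% for *u* = 3, 3/20 = 15.0% for *u* = 8, and 3/14 = 21.4% (4.7 to 50.8%) for *u* = 14. This shows sensitivity and estimates nothing.

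**The case against.** The strongest reply is that reportable events have other routes to detection. Footnote 4 allows extra thyroid tests when clinically indicated. Adverse events are assessed on Day 1 of each cycle, by contact on Day 15 of Cycles 1-3, and at the safety visit with a physical examination. Appendix 1 directs thyroid testing when endocrinopathy is suspected. Sections 11.1.1 and 11.2.1 keep most silent laboratory findings out of the tables anyway. An at-least-one-dose safety population is also conventional and consistently stated. All of this stands, and it limits the point to the narrow class in step 5.

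A reader might go further and infer that scheduled testing would reveal only 80% down to 40% of thyroid events, by supposing that 20% to 60% of subjects stop by dose two. The documents do not support that, for three reasons.

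- **Stopping rate.** The upper end would rest on 6 of 10 patients in Section 1.2.3 without response or stable disease. They received ipilimumab plus nivolumab, and no stopping times are given. This protocol allows treatment beyond RECIST progression (Section 5.1.2).
- **Equal incidence.** It would require the same event probability over 58 days as over 198. Under a constant hazard (also an assumption) with 60% stopping after two doses, the share arising in the others is 0.4×86/(0.4×86 + 0.6×58) = 50% if they receive three doses and 0.4×198/(0.4×198 + 0.6×58) = 69% if they receive seven. With 20% stopping, the same formula gives 86% to 93%.
- **Timing.** The first scan falls after Cycle 2 (±7 days) and C3D1 has a ±3-day window. The C3D1 sample may be drawn before the decision to stop, so a two-dose subject is not necessarily untested.

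A reader might also infer that the work described in Section 12.6.3 as "Exploratory analyses correlating clinical outcomes and adverse events with stool microbiome diversity/composition" would be distorted by time on treatment. That work is exploratory and optional, so this is at most a caution in interpretation.

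**Conclusion.** The gap in the schedule is real and follows from the calendar alone. A subject who stops before the C3D1 draw has no scheduled post-dose thyroid test, one who stops before C2D1 has no scheduled post-dose amylase/lipase, and a completer has neither after dose 7 unless screened for re-treatment. Because all dosed subjects remain in the denominator, the effect is under-detection of a limited class of events of special interest, greater in early stoppers.

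Its size is not derivable, since the documents give no early-stopping rate, no event rate and no frequency of symptom-driven testing. The response endpoint and the Simon design do not use these tests. An effect on the Section 12.7 stopping rule, which counts treatment-related Grade 3 or higher events, is not shown. This is a cheap improvement, not an error in the plan.

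**What to change.** In the Section 7 calendar, mark the existing thyroid panel and amylase/lipase at the safety visit, on the blood draw already taken for CBC and CMP, and amend footnote 4 to match. Every subject who attends, including one given a single dose, then has a post-dose value.

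In Section 12.6.2, keep the all-dosed rate as the main summary and add, for each assay, the number of dosed subjects with no post-dose test. A tested-only rate should not replace the all-dosed rate. It would drop early stoppers and mix scheduled with symptom-triggered tests, which brings its own selection.

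The cost is added assays at one existing visit, one extra line in the safety table and a few more laboratory findings to assess. No saving should be counted from the C1D1 thyroid test, because footnote 4 may already let the screening sample serve. No dosing or management rule changes.

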## 6.4 Protocol Therapy Discontinuation

In addition to discontinuation from therapy related to toxicities as outlined in Appendix 1, a subject will also be discontinued from protocol therapy and followed per protocol under the following circumstances outlined below. The reason for discontinuation of protocol therapy will be documented on the electronic case report form (eCRF)

- Confirmed disease progression per RECIST 1.1 prior to Cycle 7
- Completion of scheduled treatment
- Site investigator determines a change of therapy would be in the best interest of the subject
- Subject requests to discontinue protocol therapy, whether due to unacceptable toxicity or for other reasons
  - In a subject decides to prematurely discontinue protocol therapy (“refuses treatment”), the subject should be asked if he or she may still be contacted for further scheduled study assessments. The outcome of that discussion should be documented in both the medical records and in the eCRF.
- Female subject becomes pregnant.
- If subject weight falls to 35kg or less.

- Grade  $\geq 3$  infusion reaction.
- Study therapy is interrupted for  $\geq 120$  days.

Subjects who are permanently discontinued from receiving investigational product will be followed for safety per Section 7, including the collection of any protocol-specified blood specimens, unless consent is withdrawn or the subject is lost to follow-up or enrolled in another clinical study. All subjects will be followed for survival. Subjects who decline to return to the site for evaluations will be offered follow-up by phone every 3 months as an alternative.

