- 7: Urinalysis for bilirubin, blood, glucose, ketones, pH, protein, specific gravity to be performed at screening and as clinically indicated throughout the study per site investigator's discretion.
- 8: Radiology imaging to include: CT of the chest, CT or MRI of the abdomen/pelvis and bone scan (in subjects with bone metastasis). Scans should be performed at screening then every 2 months ( $\pm$  7 days) during Cycles 1-7 (e.g., after C2, C4, etc.) and then every 3 months ( $\pm$  7 days) until the time of progression. Imaging for the D30 safety visit may be omitted if already performed within 2 past months.
- 9: Tremelimumab will be given approximately every month for up to 7 cycles in the absence of disease progression or prohibitive toxicity. Refer to Section 5 for information regarding monitoring of subjects during infusion.

10: Representative formalin-fixed paraffin-embedded (FFPE) tumor specimens in paraffin blocks (blocks preferred) or at least 15 unstained slides will be identified prior to subject registration and shipped prior to C1D1. If archival tissue is not available and the subject is undergoing a standard of care biopsy, tissue from the biopsy is required to be submitted for correlative analyses. Subjects without adequate baseline tumor tissue may be considered for enrollment on a case by case basis after discussion with the sponsor-investigator. See Correlative Laboratory Manual (CLM) for additional details.

11: Surplus tissue remaining after routine standard of care procedures (e.g., metastatic biopsies) during and after treatment will be collected during this study. Subjects may have tumor tissue obtained during the course of the study or at the time of disease progression for clinical purposes (e.g., confirmation of disease progression, management of complication of disease progression, etc.). Subjects will have the option of whether samples obtained during standard of care procedures may be used for research purposes. Samples for correlative analysis are required if a standard of care biopsy is performed at screening for the first 7 cycles of treatment. See CLM for additional details.

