#### 10.1.4 Adverse Events

Risks with tremelimumab monotherapy include, but are not limited to, GI effects (colitis, diarrhea, enterocolitis and intestinal perforation), endocrine disorders (hypo and hyperthyroidism, hypophysitis and adrenal insufficiency), skin effects (rash, and pruritus), elevations in lipase and amylase and clinical manifestations of pancreatitis, other gastrointestinal

events e.g. ulcerative colitis, dehydration, nausea and vomiting; hepatic events including hepatitis, and liver enzyme elevations; pneumonitis and ILD; nervous system events including encephalitis, peripheral motor and sensory neuropathies, Guillain-Barre and proximal muscle weakness; cytopenias including thrombocytopenia, anemia and neutropenia; infusion-related reactions, anaphylaxis, and allergic reactions; renal events including renal failure, acute kidney injury, nephritis, nephrotic syndrome, autoimmune nephritis and electrolyte abnormalities such as hypokalemia; autoimmune diseases including autoimmune arthritis, Sjogren's syndrome and giant cell temporal arteritis; hyperglycemia and diabetes mellitus; and pyrexia. For information on all identified and potential risks with tremelimumab please always refer to the current version of the tremelimumab IB. Using pooled data from monotherapy clinical studies AEs (all grades) reported very commonly ( $\geq 10\%$  of patients) were diarrhea, nausea, fatigue, pruritus, decreased appetite, rash, vomiting, dyspnea, constipation, cough, pyrexia, abdominal pain, decreased weight, headache, asthenia, and anemia. Approximately 16% of patients experienced an AE that resulted in permanent discontinuation of tremelimumab and approximately 45% of patients experienced an SAE.

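### Footnote 15 assigns progression follow-up only to treatment completers while footnote 8 scans everyone until progression, so early stoppers may be imaged inconsistently and PFS, run to last contact, biased upward

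*Combined protocol and SAP*

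**What the plan says.** Four places in the protocol bear on a subject who stops tremelimumab early without progression.

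- **Section 7, footnote 15**, attached to the calendar's Follow up column: "Subjects completing study treatment without evidence of disease progression will be followed every 3 months for progression". It then covers re-treatment, and survival follow-up after progression or new therapy. It does not mention a subject who stops early and has not progressed.
- **Section 6.4**: "Subjects who are permanently discontinued from receiving investigational product will be followed for safety per Section 7", and "All subjects will be followed for survival". Tumor imaging is not named. The section opens more broadly: "a subject will also be discontinued from protocol therapy and followed per protocol under the following circumstances".
- **Section 7, footnote 8**: scans every 2 months during Cycles 1-7, then every 3 months "until the time of progression. Imaging for the D30 safety visit may be omitted if already performed within 2 past months". Nothing limits this to completers.
- **Section 9.4.6**: PFS runs to progression, resection of measurable tumor or death. For subjects still at risk it runs to the date of last contact. For duration of response, 9.4.3 and 12.2.2 give the end events but no censoring rule.

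On how many subjects might stop early, Section 10.1.4 reports from pooled monotherapy studies: "Approximately 16% of patients experienced an AE that resulted in permanent discontinuation of tremelimumab".

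**The concern.** Completing treatment and stopping treatment are different things in this protocol. Section 6.4 lists "Completion of scheduled treatment" as one reason for discontinuation among several. Section 5.1.3 ties re-treatment to patients who complete the initial seven cycles. Where everyone is meant, footnote 14 says so: "The safety follow-up visit should only occur when subjects stop study treatment for whatever reasons (toxicity, progression, or at discretion of site investigator". A site that takes footnote 15 at its word has no instruction there to follow an early stopper for progression, and 6.4 does not supply one. A site that works from footnote 8 keeps scanning.

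At stake are PFS and duration of response. If scanning ends but survival contact continues, a later progression goes undated and the subject stays progression-free on paper until death or last contact. The error runs in one direction and falls on subjects with treatment-limiting toxicity, some of whom may be responders. Section 12.1 gives durability as the reason a low response rate could still be clinically meaningful. Scans that were not taken cannot be recovered at analysis.

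**Working it through.** **1. Follow-up of a subject who stops early without progression**

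| Place | Progression imaging after stopping |
|---|---|
| Footnote 15 (Follow up column) | Assigned to completers; silent on early stoppers |
| Section 6.4 | Safety and survival named; imaging not named; lead-in refers to the protocol |
| Footnote 14 and calendar | Imaging at the 30-day visit for all stoppers, which footnote 8 allows to be omitted if done within 2 months |
| Footnote 8 | Every 3 months until progression, no restriction |

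Footnote 8 does not fully settle the matter. The calendar puts the 3-monthly scans in the column that carries footnote 15. Footnote 8's own timeline is tied to Cycles 1-7, so the interval for someone who leaves in, say, Cycle 2 is unclear.

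**2. Number of subjects**

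Inputs: N = 28, stage 1 n = 18, target response rate 15% (Section 12.3); 16% (Section 10.1.4).

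- 0.16 × 28 = 4.5 subjects. The binomial 5th to 95th percentile is 2 to 8.
- Stage 1 only: 0.16 × 18 = 2.9.
- Responders: 0.15 × 28 = 4.2. If the same 16% applies to them, 4.2 × 0.16 = 0.7 would stop for an adverse event. The chance of at least one among 4 is 1 − 0.84⁴ = 0.50.

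**3. Effect on PFS if every site reads footnote 15 narrowly**

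The documents give no PFS or OS medians, so these are assumptions:

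- exponential PFS with median m = 2, 3 or 4 months, paired with OS medians of 7, 8 and 10 months;
- adverse-event stop times uniform over seven 28-day cycles (196 days, about 6.4 months);
- last scan 1 month after stopping;
- any later progression replaced by the date of death.

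True 6-month PFS is 0.5^(6/m), and the chance that progression comes more than 1 month after stopping is 0.5^(1/m). The 16% can be read in two ways.

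- *Upper case*: all 16% stop before progression. Undated share = 0.16 × 0.5^(1/m).
- *Lower case*: 16% have a stop time, which counts only if it precedes progression. The share stopping before progression is 0.16 × [m / (6.4 ln 2)] × [1 − 0.5^(6.4/m)], which is 6.4%, 8.4% and 9.7%. Multiplying by 0.5^(1/m) gives the undated share.

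| m (months) | True 6-month PFS | Undated, upper | 6-month PFS, upper (simulated) | Undated, lower | 6-month shift, lower (simulated) |
|---|---|---|---|---|---|
| 2 | 12.5% | 11.3% | 12.4 → 17.5% (+5.1) | 4.5% | about +2 |
| 3 | 25.0% | 12.7% | 24.9 → 29.2% (+4.3) | 6.6% | about +2 |
| 4 | 35.4% | 13.5% | 35.5 → 39.2% (+3.7) | 8.1% | about +2 |

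In the lower case, 4.5% to 8.1% of 28 is 1.3 to 2.3 subjects, and median PFS moves by about 0.1 month or less.

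The standard error of 6-month PFS at n = 28 is √[p(1−p)/28] = 6.2, 8.2 and 9.0 points. The upper-case shifts are 0.8, 0.5 and 0.4 of it; the lower-case shifts are 0.2 to 0.3.

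**4. Decision rule**

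The plan's figures reproduce. With 18 then 28 subjects, stopping at 0 responses and rejecting at 3 or more, exact power at 15% is 0.803 (stated 80%) and type I error at 2% is 0.0174 (stated 0.02). Later progression follow-up does not enter this calculation.

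**The case against.** The strongest reply is that imaging is already required. Footnote 8 is express and general, and silence in footnote 15 does not revoke it. Section 6.4 never says that follow-up is only for safety and survival. It refers to follow-up per protocol. It asks a subject who refuses treatment about contact for further scheduled assessments. It expects protocol-specified blood samples, one of which is drawn at progression, and it offers phone contact only to those who decline to return. Section 9.3 asks for every effort to document progression after treatment stops, although that sentence sits in the paragraph on symptomatic deterioration.

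Most of this stands. A reader might infer that the protocol ends imaging for early stoppers, or that PFS and duration of response cannot be scored for them. The documents support neither: sites that apply footnote 8 can score both endpoints. Nor is it right that such subjects have no PFS rule. Section 9.4.6 has one, and last contact is where the bias enters.

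The size can fairly be challenged too. The 16% is a pooled historical rate, not an assumption for this trial, and may include subjects who had already progressed. It also leaves out stops by subject or investigator choice. The PFS shift assumes that every site reads narrowly; if half of the affected subjects were imaged, the lower-case shift falls to about 1 point.

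A reader might also infer a threat to the primary endpoint, because Section 9.4.2 requires a confirmatory assessment at least four weeks later and the day-30 scan can be omitted. That is possible on the narrow reading, but 9.4.2 applies whether or not treatment continues, and no effect on the count of responses has been shown.

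The objection does not remove the conflict. The column holding the post-treatment scans is governed by a footnote written for completers, and two careful sites could act differently.

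**Conclusion.** The point holds as a conflict of wording that can make progression follow-up inconsistent across sites. It is not a stated end to imaging. It concerns about 4 to 5 of 28 subjects at the historical 16%, fewer if some of them have already progressed and more once other early stops are added. With PFS run to last contact, those not imaged bias PFS upward, and the end of response may go undated for an expected 0.7 responders or so. If every site read footnote 15 narrowly, 6-month PFS would be overstated by roughly 2 to 5 points. That is below one standard error at this sample size and rests on assumed medians and stop times. PFS and duration of response are secondary and descriptive, and the Simon rule is not shown to be affected. The correction is still worth making prospectively, because the bias has a known direction and the missing scans could not be obtained later.

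**What to change.** 1. **Footnote 15**: change the opening to *Subjects who stop study treatment for any reason*, keeping the condition that they have no evidence of progression.
2. **Section 6.4**: state that permanently discontinued subjects without progression continue tumor imaging on the footnote 8 schedule until progression, in addition to safety and survival follow-up. Say which footnote 8 interval applies from the date of stopping.
3. **Section 9.4.6**: censor PFS at the last evaluable tumor assessment instead of last contact, and add the same rule for duration of response in 9.4.3 and 12.2.2.

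The cost is wording in these places and a few more follow-up scans at sites that would have read footnote 15 narrowly. No procedure is added beyond footnote 8, and the sample size and decision rule do not change.
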